10.0 PHARMACOLOGY PLAN

Women stable on an EFV and 2 NRTIs-based regimens, who are on RIF and INH, and who have not received DMPA within the last 180 days, will receive one dose of DMPA at

study entry. An optional dose of DMPA will be available at no cost to all study participants, after all week 12 study evaluations are completed. Refer to section 5.1.1 for the allowed NRTIs and section 5.4.2 for the prohibited NRTI combinations.

The primary PK analysis is described in section 9.6. The secondary PK analysis employing a population approach and nonlinear mixed effects modelling is described in this section.

10.1 Pharmacology Objectives

Using nonlinear mixed-effects (NLME) modeling, the population PK of MPA will be described in the population in order:

10.1.1 To describe the structural PK model for MPA given in the DMPA formulation.

10.1.2 To identify and quantify the effects of covariates influences on PK (eg, weight [including total, fat and lean components], age, time on TB treatment, time on ART, adherence to ART and TB treatments, CYP2B6 genotype, etc.).

10.1.3 To characterize between subject and random unexplained components of the PK variability.

10.1.4 To predict the time at which the proportion of women with MPA <0.1 ng/L matches that at 12 weeks from historical data.

10.2 Pharmacology Study Design

Doses of all ARV and TB medications taken for 48 hours prior to PK will be collected on the CRF at weeks 2, 4, 6, 8, 10, and 12. The participant should be contacted one week prior to the scheduled visit to reinforce the importance of 100% adherence to RIF and EFV and of her upcoming appointment. A participant who misses 2 or more doses of RIF and EFV within one week prior to the scheduled PK sampling at weeks 2, 4, 6, 8, 10, and 12 will have the visit rescheduled to one week later. For the week 10 and week 12 visits, the rescheduled PK sampling should be strictly within the original visit window for that visit. The schedule for the remaining visit weeks should not be changed. The rules for replacing participants who do not complete the PK are described in sections 8.1 and 9.5.

A single 4 mL blood sample for PK will be collected just prior to DMPA injection at week 0 and at the scheduled visits at weeks 2, 4, 6, 8, 10, and 12. The blood sample will be centrifuged within 1 hour of collection to separate the plasma which will be stored at -70°C or colder until assay for MPA and progesterone.

The ACTG Pharmacology Specialty Laboratory at the University of Cape Town will use liquid chromatography-tandem mass spectrometry (LC MS/MS) to measure MPA and progesterone in the plasma. The assay methods will be validated and submitted to Clinical Pharmacology Quality Assurance (CPQA) for review.

10.3 Primary and Secondary Data, Modeling, and Data Analysis

The concentration vs. time data for DMPA will be analyzed using NLME modelling using the software NONMEM (Version 7.2) [57].

The modelling approach will follow a stepwise procedure to first identify the structural model best describing the data, and then incorporate the effect of the study covariates such as weight, age, and effect of concomitant anti-retroviral and anti-tuberculosis treatment.

Various structural pharmacokinetic models will be evaluated, focusing on correctly characterizing the absorption after intra-muscular injection. The tested models will include one, two, and three compartments disposition with first-order elimination and zero-, first-order, or saturable absorption.

Statistically significant variability and correlation estimates for the PK parameters will be included and the covariates of interest will be evaluated with respect to their impact on the PK parameters and their variability.

Allometric scaling [59] will be used to account for the effect of body size on the PK parameters, using total body weight or fat-free mass. Other covariate effects will be evaluated and included if they significantly improve the ability of the model to describe the data. The effect of adherence to and time on ART and TB regimens, and CYP2B6 genotype (if available), will be investigated on clearance.

Concentrations below the limit of quantification will be included in the analysis and handled with established methods [60].

The tools used for model development and graphical and statistical diagnostics will include Xpose, and Perl Speaks NONMEM, and Pirana [61].

The PK profiles will be analyzed using post-hoc Bayesian methods to extract information such as peak concentration, overall exposure (AUC), and time above target concentration. Simulations will be employed to explore the pharmacokinetic profiles, their variability in a population, and how they are affected by weight, concomitant anti-retroviral or anti-tuberculosis treatment, other covariates found significant, and possibly under different dosing scenarios, and to predict the time at which the proportion of women with MPA <0.1 ng/L matches that at 12 weeks from historical data.

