9.4 Sample Size and Accrual

It is known that DMPA, EFV, and RIF drugs share some common metabolic pathways via the CYP3A4 enzyme system: MPA is metabolized by and induces CYP3A4 activity; RIF is primarily metabolized by CYP2B6 system but also by CYP3A4 and induces CYP3A4 and CYP2B6 enzyme activities; EFV is primarily metabolized by CYP2B6 and both induces and inhibits CYP3A4 enzyme activity (mixed and unpredictable activity). Therefore, it is anticipated that co-administration with EFV and RIF will induce clearance of MPA concentration, resulting in lower MPA concentrations during the elimination phase, compared to those seen when DMPA is administered alone. Thus, DMPA may need to be administered more frequently when used together with EFV and RIF.

The study hypothesis is that concurrent use of EFV and RIF increases the clearance of MPA, resulting in reduced MPA concentrations. The study will evaluate whether more frequent DMPA dosing is needed when DMPA is administered in combination with EFV and RIF in HIV- and TB-infected women. The evaluation of dosing frequency will be conducted by estimating the proportion of women with MPA levels <0.1 ng/mL 12 weeks post-dose (at the end of the dosing cycle). The critical value 0.1 ng/mL for MPA levels was chosen based on published papers including studies by Mishell [17] and Smit et al. [55]. These studies indicate that when MPA level falls below 0.1 ng/mL, serum progesterone level rises and the probability of ovulation increases.

In ACTG DMPA studies A5093 and A5283 in HIV-infected women, of the 79 PK evaluable participants, 5 women had MPA levels <0.1 ng/mL at 12 weeks after a single dose of DMPA was administered. None of these 5 women, however, had any evidence of ovulation (serum progesterone levels remained below 5 ng/mL). In a study by Smit et al. [56] in 94 women, all but one woman had MPA levels above 0.1 ng/mL at 12 weeks after DMPA administration. These 94 women had received either a single dose or multiple doses of DMPA. Therefore, based on the single dose studies, the proportion of women with MPA levels <0.1 ng/mL (sub-therapeutic MPA levels) 12 weeks post-dose is thought to be about 6% in normal DMPA use, although a study conducted by Trussell [57] showed that there is a contraceptive failure rate of about 0.3% when DMPA is used correctly.

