The primary analysis outcome will be the proportion of women with sub-therapeutic MPA levels (<0.1 ng/mL) at 12 weeks. A one-sided binomial test with significance level 0.05 will be used to test the null hypothesis that the proportion of women with sub-therapeutic MPA level is 6% or less. A sample size of 42 women provides 90% power to reject the null hypothesis if the proportion of women with sub-therapeutic MPA levels in this study is at least 21% (this is 15% or higher increase from the 6% threshold). With a sample size of 42 women, the underlying true proportion will be declared as statistically significant increase if 6 or more women have sub-therapeutic MPA levels at 12 weeks (this is equivalent to saying that 90% CI for the underlying proportion is entirely above the 6% threshold). Based on the results from a PK study of oral contraceptives containing ethinyl estradiol (estrogen) and norethindrone (progestin) which are metabolized by CYP3A4 enzyme [58], the study team considers that the underlying proportion of women with sub-therapeutic MPA levels of 21% or higher (15% or higher

increase from the 6% threshold) is plausible in the setting of coadministration with EFV and RIF.

The statistical power was also examined to see if the sample size will achieve a plausible power to detect a clinically meaningful decrease (30%) in MPA concentration at 12 weeks (MPA C_{min}) as one of the secondary objectives. With a significance level of 0.05, a one-sided t-test showed about 91% and 84% power to detect a 30% decline when the coefficient of variation (CV) is 60% and 70%, respectively (in the ACTG study A5093, CV of MPA C_{min} was approximately 57% when coadministered with EFV). We note that this power was examined in \log_e -scale since it is known that PK parameter C_{min} has a \log -normal distribution.

To protect against 10% loss of the primary outcomes after study accrual is closed, the study will enroll a total of 46 women. (In the ACTG DMPA study, A5093, the loss of the primary outcomes of week 12 was 9.8% [6 of 61 participants] due to either sample specimen loss or assay results not available.)

A participant is considered to be evaluable for the primary objective if the participant completes the MPA PK sampling during the study period of 12 weeks after DMPA administration. The participant replacement criteria are described in sections 8.1 and 8.2.

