9.6.1 Analyses of Primary Outcome Measurements

The proportion of participants with sub-therapeutic MPA levels (<0.1 ng/mL) will be estimated based on the participants who complete the PK sampling at 12 weeks after DMPA administration. A 90% confidence interval (CI) will be provided for proportion using Clopper-Pearson exact method for binomial measurements. This CI will provide us reasonable evidence that the true proportion is greater than the threshold (6%), by determining whether the 90% CI is entirely above the threshold.

Individual-specific MPA concentration-time curves in the elimination phase will be estimated by fitting \log_e -linear regression models to the data of MPA concentrations obtained at time of maximum MPA concentration and later. These estimated individual elimination curves will then be used to estimate the times (weeks) where MPA concentration levels reach at 0.1 ng/mL. We will present descriptive statistics of these estimated weeks including mean, SD, median, interquartile range, minimum and maximum. Mixed-effects model analysis (allowing individual elimination slope to be both fixed and random variable) with repeated measurements within individual participants will also be performed to estimate the times for comparison purposes with the results obtained using the \log -linear regression models fitted for individual participants. These modeling approaches will provide the population mean estimate of the time where MPA concentration level reaches at 0.1 ng/mL with 90% CI, which will guide us to determine optimal dosing frequency of DMPA in the study population. Details of these modeling approaches will be described in the statistical analysis plan that will be generated separately and approved by study team.

Descriptive statistics of plasma progesterone levels will be tabulated by study week. If there are participants with progesterone levels >5 ng/mL, the proportion and percentage of participants with progesterone levels >5 ng/mL will be tabulated by study week.

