10.4 Anticipated Outcomes

The anticipated outcomes are described in the section above. They are the model outputs: firstly the population PK of MPA will be described using the primary model parameters and secondary measure estimates. Covariate effects on the model parameters will be identified and quantified. The model will ascribe variability (due to fixed effects, inter individual and random unexplained variability) with accuracy. Secondly, simulations will predict the optimal dosing frequency to achieve a target trough concentration of >0.1 ng/mL in the target proportion of women.

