Statistical Analysis Plan

**ACTG A5338: An Open-Label, Non-Randomized Study of
Pharmacokinetic Interactions Among Depot Medroxyprogesterone Acetate
(DMPA), Rifampicin (RIF), and Efavirenz (EFV) in Women Co-Infected
with Human Immunodeficiency Virus (HIV) and Tuberculosis (TB)**

ClinicalTrials.gov Identifier: NCT02412436

**Version 1.0
November 28, 2018**

Introduction

This Statistical Analysis Plan addresses the following secondary objectives listed in the study protocol.

1.3.1. To estimate the area under the concentration-time curve (AUC), trough concentration (C_{\min}), maximum concentration (C_{\max}), apparent clearance (CL/F), and half-life ($t_{1/2}$) of MPA in HIV and TB coinfecting women taking EFV-based cART and RIF-containing TB treatment.

1.3.2. To estimate time and variability in time to MPA C_{\min} reaching 0.1 ng/mL or less in HIV and TB coinfecting women taking EFV-based cART and RIF-containing TB treatment.

Statistical Analysis Plan

- The concentration vs. time data for DMPA will be analyzed using nonlinear mixed-effects (NLME) modelling using the software NONMEM (version 7.4.2) (S. Beal, Sheiner, Boeckmann, & Bauer, 2009) pooling the data from the available studies A5338, A5238 and A5093.
- The modelling approach followed a stepwise procedure to first identify the structural model best describing the data, and then incorporate the effect of the study covariates such as weight, age, and effect of concomitant anti-retroviral and anti-tuberculosis treatment.
- Various structural pharmacokinetic models were evaluated, focusing on correctly characterizing the absorption after intra-muscular injection. The tested models included one and two compartments disposition, with first-order elimination and zero-, first-order, two parallel first order absorption.
- Model selection was based on changes in the NONMEM objective function value (Δ OFV), and visual inspection of conditional weighted residuals (CWRES) versus time, visual predictive checks, and basic goodness of fit plots (GOF).

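### Objective 10.1.4 and the simulation step in section 10.3 print the MPA threshold as 0.1 ng/L, 1000-fold below the 0.1 ng/mL used everywhere else

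*Protocol*

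**What the plan says.** Two places in the protocol's pharmacology plan use ng/L:

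- Objective 10.1.4: "To predict the time at which the proportion of women with MPA <0.1 ng/L matches that at 12 weeks from historical data".
- Section 10.3, end of the last sentence, on the use of the simulations: "to predict the time at which the proportion of women with MPA <0.1 ng/L matches that at 12 weeks from historical data".

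The rest of the file uses ng/mL:

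- Section 10.4, on the output of those simulations, gives a "target trough concentration of >0.1 ng/mL in the target proportion of women".
- Section 9.4 justifies 0.1 ng/mL as the critical value from published studies and reports the earlier ACTG results at that cut-off: "of the 79 PK evaluable participants, 5 women had MPA levels <0.1 ng/mL at 12 weeks". It concludes that "the proportion of women with MPA levels <0.1 ng/mL (sub-therapeutic MPA levels) 12 weeks post-dose is thought to be about 6" percent in normal use.
- Section 9.4 defines the primary analysis outcome as "the proportion of women with sub-therapeutic MPA levels (<0.1 ng/mL) at 12 weeks".
- In section 9.6.1 the fitted individual elimination curves are "used to estimate the times (weeks) where MPA concentration levels reach at 0.1 ng/mL".
- Objectives 1.2.1, 1.3.2 and 1.3.3 and sections 2.1.1, 3.0, 9.2.2.2, 9.2.2.3, 9.6.2.2 and 9.6.2.3 also use 0.1 ng/mL.
- The SAP Introduction repeats objective 1.3.2, on the time to MPA trough "reaching 0.1 ng/mL or less in HIV and TB coinfecting women". Its analysis bullets state no threshold.

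**The concern.** Objective 10.1.4 and its counterpart in 10.3 are the only specification of this prediction: find the time at which the share of women below the threshold equals the share seen at 12 weeks in historical data. The threshold is a numerical input to that calculation. A cut-off 1000 times too low would return a result of no use for dosing frequency.

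The text is current. Letter of Amendment #1 and Clarification Memo #1 both revise section 10.2, between the two affected passages, but leave 10.1.4 and 10.3 alone. The other letter and memo in the file do not touch them either. The SAP does not restate the matching step, so it does not replace the faulty wording.

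**Working it through.** **1. Size of the discrepancy.** 1 ng/mL = 1000 ng/L, so 0.1 ng/mL = 100 ng/L. The printed 0.1 ng/L is 0.0001 ng/mL, and 100/0.1 = 1000-fold.

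**2. The plan's own figures at 0.1 ng/mL.**
- Historical proportion (section 9.4): 5/79 = 6.3%, which agrees with the stated 6% or so.
- Rule of 6 or more out of 42 (section 9.4): exact one-sided alpha at 6% is 0.038, and power at 21% is 0.901 against the stated 90%. The lower limit of the 90% Clopper-Pearson interval for 6/42 is 6.41%, above 6%.

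The binomial arithmetic uses only the proportions, and the 6% comes from data reported at 0.1 ng/mL. The ng/L slip does not enter it.

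**3. Literal reading A: apply 0.1 ng/L to both sides.** Section 2.1.1 quotes week-12 MPA levels of 0.04 to 1.31 ng/mL, which is 40 to 1,310 ng/L.
- 40/0.1 = 400
- 1,310/0.1 = 13,100

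Even the lowest quoted level is 400 times the printed threshold. The historical proportion below it is effectively zero, and almost any time would match it.

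**4. Literal reading B: apply 0.1 ng/L to the simulation and match 5/79.** Inputs from section 2.1.1 are a mean week-12 level of 0.37 ng/mL and CV 57% with EFV, and an apparent half-life of about 50 days. Log-normal levels and mono-exponential decline are assumed.
- σ = √ln(1 + 0.57²) = 0.530
- μ = ln(0.37) − σ²/2 = −1.135
- The normal quantile for 5/79 is −1.528, so the 6.3rd percentile at week 12 is exp(−1.135 − 1.528 × 0.530) ≈ 0.143 ng/mL
- Halvings needed to reach 0.0001 ng/mL: log₂(0.143/0.0001) = 10.48
- Time: 10.48 × 50 ≈ 524 days after week 12, or 84 + 524 = 608 days after dosing

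Sensitivity to the mean and CV:

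| Mean (ng/mL) | CV | Days after week 12 |
|---|---|---|
| 0.45 (NRTIs only, section 2.1.1) | 53% | 543 |
| 0.37 | 57% | 524 |
| 0.37 | 70% (alternative CV in section 9.4) | 509 |
| 0.259 (0.37 × 0.7, the 30% fall in section 9.4) | 57% | 498 |

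A check without the log-normal shape: if the 6.3rd percentile at week 12 is about 0.1 ng/mL, as 5/79 implies, then log₂(1000) = 9.97 halvings, and 9.97 × 50 ≈ 498 days.

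Section 2.1.1 says MPA becomes undetectable 120 to 200 days after dosing. To fit 10.48 halvings between week 12 and day 200, the half-life would have to be (200 − 84)/10.48 ≈ 11 days, against the stated 50 or so.

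**The case against.** The best reply is that nobody would code 0.1 ng/L. Section 10.4 follows directly with the right unit for the same simulations, and section 9.4 says where 0.1 ng/mL comes from. The SAP limits itself to objectives 1.3.1 and 1.3.2 and describes much of the modelling in the past tense. That stands as a reason to rate the point minor. It does not make the text correct: the only two statements of the matching step both carry the wrong unit.

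A reader might infer more than the documents support:

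- *That the prediction is impossible.* A fitted model can return a time for any threshold, as step 4 shows. The result is meaningless, not unobtainable.
- *That the historical proportion exists only at 0.1 ng/mL.* Section 9.4 reports it only there. The SAP pools concentration data from earlier studies, so another cut-off could be calculated.
- *That 5/79 is the named target.* Both passages say only historical data. 5/79 is the natural reading, because section 9.4 bases its 6% on the single-dose studies. But section 9.4 also cites one woman of 94 in another study, and section 9.6.2.1 names the A5093 control arm as historic controls.
- *That the SAP independently fixes the threshold for this step.* Its 0.1 ng/mL is a copy of objective 1.3.2, and it does not carry the matching step.
- *That primary objective 1.2.1 is compromised because it also concerns dosing frequency.* Section 10.0 labels the population modelling secondary. Section 9.6.1 gives the primary analysis its own time-to-threshold method, in ng/mL.

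**Conclusion.** The point holds as a minor error. The threshold is printed 1000-fold too low in an operative objective and in the analysis step that serves it, almost certainly through one unit slip made twice. No calculation in the plan is wrong, and nothing in the documents shows that the printed value was used.

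The 1000-fold and 400-fold figures follow from the documents alone. The 498 to 543 days past week 12 rest on a 50-day half-life continuing unchanged and on 5/79 as the target; all but the direct check also assume a log-normal shape. That shape is rough: with mean 0.37 and CV 57% it puts 1.4% of women below 0.1 ng/mL, not 6.3%. The days are therefore indicative, but the conclusion that the time falls far beyond the detectable period does not depend on their exact value.

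The effect is confined to the secondary population-PK prediction. The primary binomial test, the sample size of 42 evaluable and 46 enrolled, and the section 9.6.1 analysis stand.

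**What to change.** Change ng/L to ng/mL in objective 10.1.4 and in the last sentence of section 10.3. Both then agree with section 10.4, the objectives, section 9 and the SAP's restatement of objective 1.3.2. The cost is two unit corrections, with no new data and no change to sample size, alpha or power. The unit change does not settle which historical proportion is to be matched; that remains as the text leaves it.

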10.4 Anticipated Outcomes

The anticipated outcomes are described in the section above. They are the model outputs: firstly the population PK of MPA will be described using the primary model parameters and secondary measure estimates. Covariate effects on the model parameters will be identified and quantified. The model will ascribe variability (due to fixed effects, inter individual and random unexplained variability) with accuracy. Secondly, simulations will predict the optimal dosing frequency to achieve a target trough concentration of >0.1 ng/mL in the target proportion of women.

10.5 Pharmacogenomics – Host Genetic Analysis

Inter-individual differences in host genes (eg, those that encode drug-metabolizing and transporter proteins) have been associated with inter-individual differences in plasma PK of EFV [38, 39, 40, 41, 42, 43] and RIF [62]. The study will therefore evaluate human genetic polymorphisms that are known to affect steady-state plasma PK of EFV and RIF. Among study participants that receive EFV and RIF, analyses of PK data will take into consideration such polymorphisms. If additional polymorphisms are reported to affect sex hormones, these may also be studied.

11.0 DATA COLLECTION AND MONITORING AND ADVERSE EVENT REPORTING

11.1 Records to Be Kept

Case report forms (CRF) will be provided for each participant. Participants must not be identified by name on any CRFs. Participants will be identified by the patient identification number (PID) and study identification number (SID) provided by the ACTG DMC upon registration.

11.2 Role of Data Management

11.2.1 Instructions concerning the recording of study data on CRFs will be provided by the ACTG DMC. Each CRS is responsible for keying the data in a timely fashion.

11.2.2 It is the responsibility of the ACTG DMC to assure the quality of computerized data for each ACTG study. This role extends from protocol development to generation of the final study databases.

